### 1.3. Sample Size and Power

A sample size of 25 evaluable subjects per arm for Part 1 and Part 2 would provide 80% power to detect a 5% difference between andecaliximab and placebo treatment in change from Baseline in FEV1 percent predicted with a 2-sided alpha level of 0.1 and a common standard deviation (SD) of 7% {Brouwer 2014, Ramsey 2011, Retsch-Bogart 2009}. Assuming an attrition rate of 15%, 30 subjects per arm were to be enrolled.

With respect to the FRI sub-study, a sample size of 15 subjects on andecaliximab and 15 subjects on placebo would provide more than 90% power to detect a 6% difference in FRI measurements (approximating an absolute change of 3% in FEV1) between the andecaliximab and the placebo arms in FRI change from Baseline, based on a 2-sample t-test and 2-sided alpha level of 0.1. The calculation assumes the SD of FRI change being 5% for the andecaliximab arm and 2% for placebo arm, as the FRI response is expected to be more heterogeneous in the treatment group.

The study was terminated after 6 subjects had been enrolled. Therefore, no inferential analyses will be performed.

## **2. TYPE OF PLANNED ANALYSIS**

### **2.1. Interim Analyses**

The first DMC safety review was planned when 10 subjects completed the Week 2 visit or discontinued early.

Due to the early study closure, the required number of subjects for the first planned DMC was not reached. Therefore, no DMC interim analyses were performed.

### **2.2. Final Analysis**

After all subjects have completed the study or discontinued early, outstanding data queries have been resolved or adjudicated as unresolvable, and the data have been cleaned and finalized, the study blind will be broken and the final analysis of the data will be performed.

### **3. GENERAL CONSIDERATIONS FOR DATA ANALYSES**

Analysis results will be presented using descriptive statistics. For categorical variables, the number and percentage of subjects in each category will be presented; for continuous variables, the number of subjects (n), mean, standard deviation (SD) or standard error (SE), median, first quartile (Q1), third quartile (Q3), minimum, and maximum will be presented.

By-subject listings will be presented for all subjects in the All Randomized Analysis Set and sorted by subject ID number, visit date, and time (if applicable). Data collected on log forms, such as AEs, will be presented in chronological order within the subject. The treatment group to which subjects were randomized will be used in the listings. Age, sex at birth, race, and ethnicity will be included in the listings, as space permits.

#### **3.1. Analysis Sets**

Analysis sets define the subjects to be included in an analysis. Analysis sets and their definitions are provided in this section. The analysis set will be identified and included as a subtitle of each table, figure, and listing.

For each analysis set, the number and percentage of subjects eligible for inclusion will be summarized by treatment group.

##### **3.1.1. All Randomized Analysis Set**

The All Randomized Analysis Set includes all subjects who were randomized in the study.

##### **3.1.2. Full Analysis Set**

The Full Analysis Set (FAS) includes all subjects who were randomized into the study and took at least 1 dose of study drug. This is the primary analysis set for efficacy analyses.

##### **3.1.3. Safety Analysis Set**

The Safety Analysis Set includes all subjects who took at least 1 dose of study drug. This is the primary analysis set for safety analyses.

#### **3.2. Subject Grouping**

For analyses based on the FAS, subjects will be grouped according to the treatment to which they were randomized.

For analyses based on the Safety Analysis Set, subjects will be grouped according to the randomized treatment except when their actual treatment differs from randomized treatment for the entire treatment duration. In this case, subjects will be grouped based on actual treatment received.

### **3.3. Strata and Covariates**

No stratification factors or covariates will be used in the analyses supporting synoptic CSR.

### **3.4. Examination of Subject Subgroups**

There will be no subgroup analyses.

### **3.5. Multiple Comparisons**

Adjustments for multiplicity will not be applied, as no inferential analyses will be performed.

### **3.6. Missing Data and Outliers**

#### **3.6.1. Missing Data**

In general, missing data will not be imputed unless methods for handling missing data are specified. Exceptions are presented in this document.

For missing last dosing date of study drug, imputation rules are described in Section 4.2.1. The handling of missing or incomplete dates for AE onset is described in Section 7.1.5.2.

#### **3.6.2. Outliers**

Outliers will be identified during the data management and data analysis process, but no sensitivity analyses will be conducted. All data will be included in the data analysis.

### **3.7. Data Handling Conventions and Transformations**

In general, age (in years) on the date of the first dose of study drug will be used for analyses and presentation in listings. If an enrolled subject was not dosed with any study drug, the randomization date will be used instead of the first dosing date of study drug. If only the birth year is collected on the CRF, “01 July” will be used for the unknown birth day and month for the purpose of age calculation. If only birth year and month are collected, “01” will be used for the unknown birth day.

### **3.8. Analysis Visit Windows**

#### **3.8.1. Definition of Study Day**

Study Day will be calculated from the first dosing date of study drug and derived as follows:

- For postdose study days: Assessment Date – First Dosing Date + 1
- For days prior to the first dose: Assessment Date – First Dosing Date

Therefore, study Day 1 is the day of first dose of study drug administration.

For the outputs based on the study period (double-blind and open-label), the following rule will be applied:

- If subject continues into open-label (OL) period then the double-blind period reports will include the data collected until the date of the first dose of study drug in OL period (Week 8) – 1 day. The open-label period summaries will include the data from the date of the first dose of OL treatment, inclusive.
- If subject does not continue into OL period then all data collected starting from Day 1 will be included in the double-blind period summaries.

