6.1.5. Week 8 (-3 to + 4): Primary Endpoint and Open-Label Extension

All Week 8 tests and procedures must be completed prior to participating in the OLE and dosing as indicated in [Table 6-1](#).

Subjects who agree to participate in the OLE portion of the study will be entered into the IXRS to confirm enrollment into the open-label extension after all other procedures as indicated in [Table 6-1](#). The first dose of open-label GS-5745 should be dispensed as directed by IXRS and administered to the subject at Week 8. Sites should train the subject on administration of the study drug at this visit. Subjects will be observed for 30 minutes after the last injection for the first 2 doses.

If the home health option is utilized during OLE, subjects will be dispensed GS-5745 at the visit prior to the scheduled home health visit for Weeks 11, 13 to 15, 17 to 19 and 21 to 23.

Subjects who do not agree to participate in the OLE portion of the study will be discontinued from the study and will be asked to return to the clinic in 30 days for their 30-day Follow-up visit as indicated in [Table 6-1](#).

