#### 7.2.2.2. Summaries of Laboratory Abnormalities

The summaries (number and percentage of subjects) for treatment-emergent laboratory abnormalities will be provided by lab test, treatment group and study phase; subjects will be categorized according to the most severe postbaseline abnormality grade for a given lab test.

For all summaries of laboratory abnormalities, the denominator is the number of subjects with nonmissing postbaseline values within study period.

A by-subject listing of treatment-emergent laboratory abnormalities will be provided by subject ID number and visit in chronological order. This listing will include all test results that were collected throughout the study for the lab test of interest, with all applicable severity grades displayed.

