- n Study drug dosing will occur at Week 8 only for subjects who elect to enroll in the open-label extension and only after all other procedures have been completed.
- o Subjects enrolled into the open-label extension may request assistance administering the SC injections either by returning to the clinic or utilizing a home health care service provided by the Sponsor to ensure proper dosing and adherence. If determined acceptable by the DMC, home self-administration may be conducted in the OLE.
- p PEFR will be performed at Baseline only if baseline procedures are conducted over 2 days and induced sputum was conducted on Day -1 to confirm subjects are stable enough to be dosed.
- q As screening will occur over at least two different days, subjects should only be asked to withhold these medications the morning of their screening spirometry assessment and only after they have been properly consented.
- r To be conducted at the site's local lab.

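### SAP 3.8.1 counts the whole date of the first open-label dose as open-label, so pre-dose Week 8 labs of extension entrants land in the wrong phase of the lab-abnormality table

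*SAP*

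**What the plan says.** SAP 3.8.1 sets the period boundary for every output split into double-blind and open-label. For a subject who continues into the extension, "double-blind period reports will include the data collected until the date of the first dose of study drug in OL period (Week 8", less one day. The next sentence sets the other side: "The open-label period summaries will include the data from the date of the first dose of OL treatment, inclusive." For everyone else, "If subject does not continue into OL period then all data collected starting from Day 1 will be included in the double-blind period summaries." The rule works on dates and has no clock-time or pre-dose exception.

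The order of events at Week 8 is fixed elsewhere. Protocol 6.1.5 states that "The first dose of open-label GS-5745 should be dispensed as directed by IXRS and administered to the subject at Week 8", and also that "All Week 8 tests and procedures must be completed prior to participating in the OLE and dosing". Footnote n of the schedule in SAP Appendix 1 agrees: "Study drug dosing will occur at Week 8 only for subjects who elect to enroll in the open-label extension and only after all other procedures" are finished.

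The output at issue is in SAP 7.2.2.2. Counts and percentages of subjects with "treatment-emergent laboratory abnormalities will be provided by lab test, treatment group and study phase", by worst post-baseline grade, and "the denominator is the number of subjects with nonmissing postbaseline values within study period".

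**The concern.** A Week 8 blood sample taken on the day of the first open-label dose is by design a pre-dose sample. It reflects blinded treatment only, but the date rule labels it open-label. Two things follow.

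- **Wrong phase.** An abnormality that first appears, or reaches its worst grade, at Week 8 is reported under open-label although no open-label drug had been given. For a subject randomized to placebo, it would be reported in an active-treatment phase before any active dose.
- **Unequal handling.** The same scheduled draw is double-blind for a subject who declines the extension and open-label for one who accepts. The phase then depends on a choice made after randomization, and the double-blind results cover a shorter stretch of follow-up for entrants than for non-entrants.

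**Working it through.** The plan gives no figure to reproduce here. The check applies the rule to the schedule.

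**Inputs**

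- Post-baseline CBC and chemistry draws: Weeks 2, 4, 8 and 16, and the follow-up visit (Protocol Synopsis, Safety Laboratory Tests).
- Nominal days: Week 2 = Day 15, Week 4 = Day 29, Week 8 = Day 57, Week 16 = Day 113 (schedule of assessments in both documents).
- First open-label dose: at the Week 8 visit, after all other procedures (Protocol 6.1.5; SAP Appendix 1, footnote n).
- Enrolled: 6 subjects (SAP 1.3). The number who entered the extension is not given.

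**Step 1: the cut-off.** Last double-blind day = date of first open-label dose − 1 = 57 − 1 = Day 56. A pre-dose draw on Day 57 is after Day 56, so it is open-label. The visit window does not change this, because the cut-off moves with the dose date.

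**Step 2: where each scheduled draw falls when labs and dose share a date**

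| Subject and rule | Double-blind | Open-label |
|---|---|---|
| Entrant, SAP as written | Weeks 2, 4 (2 draws) | Weeks 8, 16, follow-up (3 draws) |
| Entrant, Week 8 kept double-blind | Weeks 2, 4, 8 (3 draws) | Week 16, follow-up (2 draws) |
| Non-entrant, SAP as written | Weeks 2, 4, 8, follow-up | none |

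One draw moves per affected entrant: 1 of the 3 scheduled under blinded treatment. If the open-label dose is given on a later date (for example labs on Day 57, dose on Day 58), the last double-blind day is 58 − 1 = Day 57 and nothing moves.

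**Step 3: range over the study.** Scheduled subject-draws under blinded treatment are at most 6 × 3 = 18. Those moved run from 0 (no entrants, or all dosed on a later date) to 6 × 1 = 6, that is 0/18 to 6/18.

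**Step 4: effect on the table, for any one lab test**

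- *Double-blind count:* falls by at most 1 per affected entrant, and only if the abnormality was absent at Weeks 2 and 4 and at any other earlier post-baseline sample. The grade category changes only if Week 8 gave the worst grade.
- *Open-label count:* rises by at most 1 per affected entrant, and only if the abnormality is absent from later open-label results. If it persists, the subject is counted as open-label under either rule.
- *Double-blind denominator:* loses an affected entrant only if there is no post-baseline result before Week 8.
- *Open-label denominator:* gains an affected entrant only if there are no Week 16, early-termination or follow-up labs.

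**Step 5: does another rule rescue it?**

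- SAP 3.8.2 uses the nominal visit, but only for summaries by visit. The table in 7.2.2.2 is by phase.
- SAP 7.1.6 places events relative to the first open-label dose, but covers adverse events only.
- SAP 3.8.3 accepts a value on the first dosing date as Baseline. That shows the SAP can treat a same-date value as pre-dose, but it is not a period rule.

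None applies to these labs.

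**The case against.** The strongest reply is that this is an explicit, unambiguous convention, not a contradiction. A programmer has one instruction to follow, and a single date boundary shared with the adverse-event rule is common and defensible. Moving the Week 8 labs alone could put a laboratory abnormality in double-blind while an adverse event with onset on the same date is open-label.

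The practical effect may also be nil. It needs an entrant, a shared date, and an abnormality not seen before Week 8; the draw counts above are not counts of reported abnormalities. The table is also split by treatment group. If the open-label display keeps the randomized grouping of SAP 3.2, a placebo subject's Week 8 abnormality would still sit with the placebo-randomized group. With 6 subjects and full listings, a reader can see the timing directly.

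Most of this stands as a limit on importance, and it is why the point is minor. It does not make the attribution right. A date-only boundary suits adverse events, whose order relative to a same-day dose may be unknown. For Week 8 labs the protocol fixes the order, so that reason is absent. The possible mismatch with a same-date adverse event is real, but it follows from what is known about each record. A correct listing does not correct the summary table.

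**Conclusion.** The concern holds, as a minor point. As written, SAP 3.8.1 assigns to open-label those Week 8 laboratory results that the protocol requires to be obtained before the first open-label dose, and it treats entrants differently from non-entrants.

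The size is one of three scheduled blinded-treatment draws per affected entrant, for 0 to 6 subjects. This assumes that the protocol's order of procedures was followed and that labs and dose fell on the same date.

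The consequences are limited. SAP 7.2.2.1 judges emergence against Baseline at any post-baseline time point up to 30 days after the last dose, so the abnormality is relabelled and not lost. The listing in 7.2.2.2 shows all results for the test by visit. FEV1 is presented by time point (SAP 6.1.2 and 6.2.2), where the nominal-visit rule applies. SAP 1.3 rules out inferential analyses.

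**What to change.** Add one sentence to SAP 3.8.1: assessments recorded under the nominal Week 8 visit belong to the double-blind period for all subjects, whether or not they enter the extension. Apply it to both the counts and the denominators in 7.2.2.2, and to any other assessment output split by period. No clock-time rule is needed, because these assessments are pre-dose by protocol. Leave the adverse-event rule in 7.1.6 as it is. Say also that unscheduled samples on the dose date, which have no nominal visit, stay under the date rule.

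The cost is that sentence and a programming flag on the nominal visit, with no new data. SAP section 1 has later changes documented in the study report, so the correction can be recorded there if the SAP is already final.

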### **3.8.2. Analysis Visit Windows**

The nominal visit as recorded on the CRF will be used when data are summarized by visit. Any data relating to unscheduled visits will not be assigned to a particular visit or time point. However, the following exceptions will be made:

- An unscheduled visit prior to the first dosing of study drug may be included in the calculation of the baseline value, if applicable.
- For subjects who prematurely discontinue from the study, early termination (ET) data will be assigned to what would have been the next scheduled visit where the respective data were scheduled to be collected.
- Data collected on 30-day follow-up visit will be summarized as a separate visit, and labeled as “Follow-up Visit”.

### **3.8.3. Selection of Data in the Event of Multiple Records in an Analysis Visit Window**

Pre-bronchodilator FEV1 and post-bronchodilator FEV1 are considered as 2 separate measurements.

If multiple, valid nonmissing, continuous measurements exist in an analysis window, records will be chosen based on the following rules if a single value is needed:

- In general, the baseline value will be the last nonmissing value on or prior to the first dosing date of study drug, unless specified differently. If multiple measurements occur on the same day, the last nonmissing value prior to the time of first dosing of study drug will be considered as the baseline value. If these multiple measurements occur at the same time or the time is not available, the average of these measurements (for continuous data) will be considered the baseline value.

If multiple, valid nonmissing, categorical measurements exist in an analysis window, records will be chosen based on the following rules if a single value is needed:

- For baseline, the last available record on or prior to the date of the first dose of study drug will be selected. If there are multiple records with the same time or no time recorded on the same day, the value with the lowest severity will be selected.
- For postbaseline visits, if there are multiple records with the same time or no time recorded on the same day, the value with the worst severity within the window will be selected.

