3.3.3. Open-Label Extension (OLE)

On the Week 8 visit (-3 to + 4 days) of both Part 1 and Part 2, subjects (active and placebo) will be invited to participate in an OLE treatment period.

- Subjects choosing to participate from Part 1 will receive open-label 600 mg of GS-5745 weekly for 16 additional weeks.
- All subjects choosing to participate from Part 2 will receive open-label 300 mg of GS-5745 weekly for 16 additional weeks.

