#### **4.2.1. Duration of Exposure to Study Drug**

Total duration of exposure to study drug will be defined as last dosing date minus first dosing date plus 7, regardless of any temporary interruptions in study drug administration, and will be expressed in days. If the last study drug dosing date is missing, the latest study drug end date, clinical visit date, laboratory sample collection date, or vital signs assessment date that occurred during the on-treatment period will be used.

The total duration of exposure to study drug will be summarized using descriptive statistics and using the number (ie, cumulative counts) and percentage of subjects exposed through the following time periods: baseline (Day 1), Week 1 (Day 8), Week 4 (Day 29), Week 8 (Day 57), Week 12 (Day 85), Week 16 (Day 113), Week 20 (Day 141), and Week 24 (Day 169). Summaries will be provided by treatment group for the Safety Analysis Set. No formal statistical testing is planned.

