#### **6.1.2. Analysis of the Primary Efficacy Endpoint**

The descriptive statistics (n, mean, standard deviation [SD], median, Q1, Q3, minimum, and maximum) for the absolute values and absolute change in pre-bronchodilator FEV1 percent predicted will be presented for each post-baseline time point including open-label period.

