#### 7.2.2.1. Treatment-Emergent Laboratory Abnormalities

Treatment-emergent laboratory abnormalities are defined as values within the reference range at baseline, but which become lower or higher than the reference range or values had a directional change in abnormality from baseline (eg, the value low at baseline became high at postbaseline visit) at any postbaseline time point, up to and including the date of last dose of study drug plus 30 days. If the relevant baseline laboratory value is missing, any postbaseline laboratory value that is lower or higher than the reference range will be considered treatment emergent.

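### With one Day 1 baseline for all periods, the SAP's open-label lab table can misplace abnormalities, and its open-label FEV1 changes are cumulative, for placebo subjects who cross over

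*SAP*

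**What the plan says.** **Baseline.** SAP 3.8.3 gives the rule for continuous data: "In general, the baseline value will be the last nonmissing value on or prior to the first dosing date of study drug". The rule for categorical data has the same anchor: "For baseline, the last available record on or prior to the date of the first dose of study drug will be selected". SAP 3.8.1 ties that date to the start of the study ("Therefore, study Day 1 is the day of first dose of study drug administration"), and the exposure intervals in SAP 4.2.1 begin with "baseline (Day 1), Week 1 (Day 8"). The continuous rule leaves room for exceptions, but neither the FEV1 sections (6.1, 6.2) nor the laboratory sections (7.2) make one for the open-label period.

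**Crossover.** Under Protocol 3.3.3, at Week 8 "subjects (active and placebo) will be invited to participate in an OLE treatment period". For Part 1, the only part that ran: "Subjects choosing to participate from Part 1 will receive open-label 600 mg of GS-5745 weekly for 16 additional weeks".

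**Use of the baseline after Week 8.** SAP 6.1.2 says the values and changes in pre-bronchodilator FEV1 percent predicted "will be presented for each post-baseline time point including open-label period", and SAP 6.2.2 does the same for the secondary FEV1 changes. SAP 7.2.2.1 defines treatment-emergent laboratory abnormalities as "values within the reference range at baseline, but which become lower or higher than the reference range", plus reversals of direction, at any time point after baseline. SAP 7.2.2.2 then tabulates them by lab test, treatment group and study phase.

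**Period split.** SAP 3.8.1 ends double-blind data on the day before the first open-label dose and starts open-label data on the date of that dose. Protocol 6.1.5 and footnote n of the assessment schedule put all other Week 8 procedures before that dose.

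**The concern.** For a subject randomized to placebo, the first dose of study drug is a placebo dose. The last observation before any andecaliximab is at Week 8, not Day 1. A table headed as the open-label phase will be read as describing what happened on andecaliximab, but for these subjects the reference point lies eight weeks before the drug was started.

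The laboratory table matters most. SAP 7.2.1 drops descriptive statistics for laboratory tests, so the treatment-emergent table is the only laboratory summary. AEs are handled differently: SAP 7.1.6 assigns them to a phase by onset relative to the first open-label dose. Laboratory abnormalities have no matching onset rule, so the same report would attribute AEs and labs to a phase by different logic.

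For FEV1, eight weeks on andecaliximab in a former placebo subject runs from Week 8 to Week 16. The plan has no row that shows this change directly.

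**Working it through.** The point concerns a definition, so the plan states no figure to reproduce. The rules can be traced through example sequences. All subject values below are invented for illustration.

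**1. Which date anchors the baseline?** SAP 3.8.1 names the first dose in the open-label period separately from the first dose of study drug. The latter, used in 3.8.3, must therefore be Day 1, including for subjects on placebo.

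**2. Laboratory rule.** Safety labs are scheduled at Baseline, Weeks 2, 4, 8 and 16, and follow-up (Protocol synopsis and Table 6-1). For a placebo subject who crosses over, judge the Week 16 value against each candidate baseline:

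| Day 1 | Week 8, pre-dose | Week 16 | Emergent against Day 1 (SAP) | Emergent against Week 8 |
|---|---|---|---|---|
| normal | normal | high | yes | yes |
| normal | high | high | yes | no |
| high | normal | high | no | yes |
| high | high | high | no | no |

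The second row began on placebo but appears as an open-label abnormality. The third row recurred on drug but is not counted.

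**3. Week 8 date rule.** Take normal on Day 1, high at Week 8 before dosing, and normal at Week 16. If the Week 8 sample and the first open-label dose share a date, SAP 3.8.1 puts the sample in the open-label period. It is then an open-label treatment-emergent abnormality, although the subject had received only placebo when it was drawn.

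**4. FEV1.** For a former placebo subject,

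change from Day 1 to Week 16 = (Week 8 − Day 1, on placebo) + (Week 16 − Week 8, on andecaliximab).

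- Values 60, 57, 62: the SAP reports 62 − 60 = +2 points. The change on drug is 62 − 57 = +5 points.
- Values 60, 63, 63: the SAP reports 63 − 60 = +3 points. The change on drug is 63 − 63 = 0.

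Relative change divides by the Day 1 value (SAP 6.2.1). In the first example the SAP reports 2/60 = +3.3% at Week 16 and −3/60 = −5.0% at Week 8. Subtracting these gives 8.3, whereas the relative change on drug is 5/57 = 8.8%.

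**5. What is not touched.** The primary and secondary endpoints run from Baseline to Week 8 (SAP 6.1, 6.2.1), for which Day 1 is the correct baseline. The AE summaries (SAP 7.1.6) use onset dates and no baseline value.

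**The case against.** The strongest reply is that little depends on this. The SAP supports a synoptic report on 6 subjects, with no inferential analysis (SAP 1.3, 3.5, 6.1.1). Change from Day 1 is a legitimate cumulative summary. The FAS is grouped by randomized arm (SAP 3.2), so former placebo subjects need not be pooled with continuing-active subjects. The Week 8 row appears with the later rows, so absolute change since Week 8 can be found by subtraction. Laboratory listings flag every out-of-range value by visit whatever the baseline (SAP 7.2), and with 6 subjects they can be read by eye. The high/normal/high pattern is also uncounted in the active arm, and recurrence of an abnormality that preceded all dosing is not clearly a drug effect.

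Most of this stands and sets the size of the point. Three qualifications remain. Subtracting mean changes is exact only when the same subjects contribute at both visits, and it fails for relative change. The listings let a reader correct the laboratory table but do not make the table right. In the active arm Day 1 is the last pre-drug status; in the placebo arm it is not, so the same rule means different things in the two arms.

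A reader might infer that the open-label rows fail both the FEV1 and the safety objectives. The documents do not support that. The FEV1 objectives concern eight weeks of treatment and are served by the Week 8 endpoints. The principal safety output is the AE tables, which are split correctly.

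A reader might also divide the planning SD of 7 points by the square root of the number crossing over and offer the result as the size of the distortion. That quantity is sampling noise around zero drift, not bias. A Week 8 baseline would not remove noise of that kind, and the number crossing over is not given.

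**Conclusion.** The point holds in limited form. For any placebo subject who enters the OLE, the phase-split laboratory table can attribute placebo-period abnormalities to open-label andecaliximab and can omit some that recur on drug. The open-label FEV1 changes are cumulative and do not directly show change on drug. The date rule in SAP 3.8.1 adds to the laboratory problem by moving pre-dose Week 8 records into the open-label phase.

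No numerical size can be given from the documents. They do not say how many of the 6 subjects were on placebo or whether any of those entered the OLE; if none did, there is no practical effect. The conclusion rests on reading study drug in 3.8.3 as including placebo, which the wording of 3.8.1 supports. It is a correction worth making to a descriptive SAP and does not threaten the trial's endpoints.

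**What to change.** - **SAP 3.8.3:** for subjects randomized to placebo who enter the OLE, define an open-label baseline as the last nonmissing value before the first open-label dose. Subjects randomized to andecaliximab keep the Day 1 baseline.
- **SAP 7.2.2.1 and 7.2.2.2:** use that baseline for these subjects' open-label treatment-emergent laboratory abnormalities.
- **SAP 6.1.2 and 6.2.2:** add a row of open-label FEV1 change from that baseline, labelled by randomized arm, and keep the change from Day 1.
- **SAP 3.8.1:** state that Week 8 assessments taken before the first open-label dose on the same date belong to the double-blind period. Without this, one record would be both the open-label baseline and open-label data.

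The cost is one extra derived baseline and one extra row per FEV1 table, with the two arms' open-label baselines clearly labelled because they differ. No new data are needed, since Week 8 spirometry and labs are already scheduled before the open-label dose.
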